### 9.2 Subject Accountability

The number (and percent) of subjects who were enrolled, received AMG 330 and pembrolizumab and ended the study will be summarized. The number (and percent) of subjects who discontinue each treatment and the study along with the reasons for discontinuation will be summarized. Also, the date that the first subject and last subject was enrolled will be presented based on the enrolled subjects.

### 9.3 Important Protocol Deviations

Important Protocol Deviations (IPDs) categories are defined by the study team before the first subject's initial visit and updated during the IPD reviews throughout the study prior to database lock. These definitions of IPD categories, subcategory codes, and

presented.

Protocol Number: 20170646

**Date:** 25 August 2020 Page 20 of 35

descriptions will be used during the course of the study. Eligibility deviations are defined in the protocol.

## 9.4 Demographic and Baseline Characteristics

The following demographic and baseline characteristics will be summarized using descriptive statistics. If multiple races have been reported for a subject, the subject will be categorized as multiple race as well as by the combination of race.

The baseline characteristics to be summarized include:

- Sex: Male, Female
- Age: < 65, ≥ 65 to < 75, ≥ 75
- Race: American Indian or Alaska Native, Asian, Black or African American, Native Hawaiian or Other Pacific Islander, White, Other
- Eastern Cooperative Oncology Group (ECOG) performance status (Appendix C)
- Prior HSCT: Yes, No
- Response to prior therapies : Yes, No
- ELN Classification of AML (at initial diagnosis and at study entry)
- Type of AML (at initial diagnosis and at study entry)
- White blood cell count
- Absolute Neutrophil count
- Height
- Weight
- Platelet count
- Percentage of bone marrow blast

# 9.5 Efficacy Analyses

Analysis of efficacy endpoints will be based on the Safety Analysis Set unless otherwise specified.

### 9.5.1 Analyses of Primary Efficacy Endpoint(s)

No efficacy parameter is considered in primary endpoints.

### 9.5.2 Analyses of Secondary Efficacy Endpoint(s)

The percentage of subjects with a response (CRMRD-, CR, CRi, MLFS, or PR) to treatment using the European Leukemia Net (ELN) Response Criteria in Acute Myeloid Leukemia (AML) (2017) will be summarized with an exact 80% confidence interval (CI) overall and by cohort. It will be presented using an exact method proposed by Clopper and Pearson (1934). Subjects missing post baseline disease assessments will be considered not to have achieved response.

Protocol Number: 20170646

**Date:** 25 August 2020 Page 21 of 35

Duration of response will be presented per subject and Kaplan-Meier (KM) estimates may be presented.

# 9.5.3 Analyses of Exploratory Efficacy Endpoint(s)

## 9.6 Safety Analyses

## 9.6.1 Analyses of Primary Safety Endpoint(s)

Subject incidence of DLT will be summarized overall and by planned cohort. The DLT summary will be based on the DLT evaluable analysis set.

The statistical analysis methods for other safety endpoints are described in Section 9.6.2 to Section 9.6.6.

#### 9.6.2 Adverse Events

The Medical Dictionary for Regulatory Activities (MedDRA) version 23.0 or later will be used to code all events categorized as adverse events to a system organ class and a preferred term.

The subject incidence of adverse events will be summarized for all treatment-emergent adverse events, treatment-related adverse event, serious adverse events, grade 3 and above adverse events, adverse events leading to withdrawal of investigational product, and fatal adverse events. Also subject incidence of adverse event may be summarized by dose step.

Subject incidence of all treatment-emergent adverse events, treatment-related (AMG 330 related, pembrolizumab related and in combination of AMG 330 with pembrolizumab related) adverse events, serious adverse events (SAEs), grade 3 and above adverse events, adverse events leading to withdrawal of investigational product, and fatal adverse events will be tabulated by system organ class and preferred term in decreasing order of frequency. In addition, treatment-emergent adverse events and treatment-related adverse events will be summarized by system organ class, preferred term, and worst grade. Also SAEs and grade 3 and above will be summarized by preferred term only in descending order of frequency. The severity of each adverse event will be graded using Common Terminology Criteria for Adverse Events (CTCAE) version 5.0 criteria with the exception of cytokine release syndrome (CRS), which must

Protocol Number: 20170646

Date: 25 August 2020 Page 22 of 35

be graded using the criteria referenced in the publication by Lee et al (2014), and tumor lysis syndrome (TLS), which must be graded using the Cairo-Bishop criteria.

Treatment-emergent events of interest (EOIs) will be summarized by EOI category and preferred term. Subject incidence by PT and the worst grade will be summarized for selected EOIs. CSR symptoms will also be summarized.

## 9.6.3 Laboratory Test Results

Clinical chemistry, hematology, and urinalysis data will be reviewed for each subject.

Shift tables between the worst post-baseline and baseline grades for selected laboratory parameters may be provided.

### 9.6.4 Vital Signs

Vital signs will be listed and reviewed for each subject in dose level review meeting (DLRM). The analyses of vital signs including summary statistics over time and/or changes from baseline over time may be provided. The number and percentage of subjects with abnormal changes (defined in Appendix B, Table 14-1) in systolic blood pressure, diastolic blood pressure, temperature and heart rate may be summarized.

# 9.6.5 Physical Measurements

Physical measurements will be reviewed for each subject in DLRM. Summary statistics over time may be provided.

#### 9.6.6 Electrocardiogram

All on-study electrocardiogram (ECG) data parameter (QRS, QT, QTc, RR, and PR intervals) will be listed and during the analysis one or all of these parameters will be plotted.

Summaries over time and/or changes from baseline over time will be provided for all ECG parameters. Subjects' maximum change from baseline in QTc will be categorized and the number and percentage of subjects in each group will be summarized. Subjects' maximum post baseline values will also be categorized and the number and percentage of subjects in each group will be summarized.

Summaries over time and/or changes from baseline over time will be provided for all 12-lead ECG parameters. The analysis of Fridericia's (QTcF) QT correction and Bazett's (QTcB) QT correction will be performed using the derived results as specified in Section 5.2.

Protocol Number: 20170646

**Date:** 25 August 2020 Page 23 of 35

Subjects will be categorized into the following groups per their maximum change from baseline in QTcF and QTcB. Unscheduled assessments will be included in the determination of the maximum change.

- ≤ 30 msec
- > 30 60 msec
- > 60 msec

The number and percentage of subjects in each group will be summarized. A listing of the subjects with > 60 msec change from baseline in QTcF and QTcB will be provided.

Subjects will also be categorized into the following groups per their maximum post baseline QTcF and QTcB. Unscheduled assessments will be included in the determination of the maximum post baseline value.

- ≤ 450 msec
- > 450 480 msec
- > 480 500 msec
- > 500 msec

The number of subjects in each group will be summarized for each dosing group. A listing of the subjects with > 500 msec post baseline in QTcF and QTcB will be provided.

## 9.6.7 Antibody Formation

The incidence and percentage of subjects who develop anti-AMG 330 antibodies (binding and if positive, neutralizing) and anti-pembrolizumab antibodies at any time will be tabulated overall and by cohort.

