## 3.1.1 Cohort 1 Design

Cycle 1 is 77 days in duration and subsequent cycles are 57 days. Treatment will start with AMG 330 on day 1. Dexamethasone 8 mg will be given to subjects 1 hour prior to each step dose of AMG 330. AMG 330 will be administered at a starting dose of µg/day for 3 days, followed by µg/day for 4 days, followed by µg/day for 7 days. If the subject experiences DLT during these first 7 days of treatment with AMG 330 at µg/day, this subject will be replaced. If the subject has not experienced a DLT by day 14, they will receive pembrolizumab on day 15. Pembrolizumab will be administered at a dose of 200 mg (Q3W) by a 30-minute IV infusion. The subject will remain at an AMG 330 dose level of µg/day for additional 7 days.

Thereafter, AMG 330 dosing will continue as per Table 3-1, increasing dose levels to µg/day for 7 days followed by µg/day for 7 days. If the subject has not experienced a DLT at the µg/day dose level of AMG 330 between days 29 to 35, they will receive pembrolizumab on day 36 and remain on the AMG 330 µg/day dose for an additional 7 days. AMG 330 dosing will further increase to µg/day for 7 days followed by µg/day for 7 days. If the subject has not experienced a DLT at the µg/day dose level of AMG 330 between days 50 to 56, they will receive pembrolizumab on day 57 and remain on the µg/day dose for additional 7 days. To complete cycle 1, a final dose level increase to µg/day AMG 330 for an additional 14 days will be administered.

Cycle 1 will be followed by a 1-week interval without AMG 330 administration and administration of pembrolizumab will continue non-interrupted on the Q3W schedule. The AMG 330-infusion free interval may be extended up to 4 weeks (depending on safety, treatment response, and in case of prolonged marrow aplasia and cytopenia in aleukemic subjects) after consultation with the sponsor.

Cycle 2 will start with the initiation of AMG 330 administration and include the same step dose levels and duration as in cycle 1 with the exception of the and pg/day dose levels, which will be shortened from 14 days to 7 days (Table 3-2). The duration of AMG 330 step dose levels in cycle 2 and beyond can be shortened to 2 to 5 days if a subject tolerated the investigational product in cycle 1 and based on the discussion and agreement between the investigator and the sponsor. All subsequent cycles will be conducted similarly to cycle 2.

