## 6. Analysis Sets

The analysis of all endpoints, unless noted otherwise, will be conducted on the Safety Analysis Set defined in Section 6.1

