### 6.1 Safety Analysis Set

Safety Analysis Set defined as all subjects that are enrolled and receive at least 1 dose of AMG 330 or pembrolizumab.

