## 6.3 Pharmacokinetic Analyses Set(s)

The PK Analysis Set will contain all subjects who have received at least 1 dose of the AMG 330 or pembrolizumab and have at least 1 PK sample collected.

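### SAP 9.6.7 sets no drug-specific, sample-based denominator for antibody incidence, so the default Safety Analysis Set can dilute the percentage

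*SAP*

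**What the plan says.** SAP 9.6.7 tabulates the number and percentage of subjects developing antibodies to each drug. For the second drug the text reads "anti-pembrolizumab antibodies at any time will be tabulated overall and by cohort". The section names no analysis set, sample requirement or rule for missing results. Protocol 9.4.2.3.7 covers anti-AMG 330 only and names no denominator either.

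The default is in SAP section 6: "The analysis of all endpoints, unless noted otherwise, will be conducted on the Safety Analysis Set defined in Section 6.1". SAP 6.1 defines that set as "all subjects that are enrolled and receive at least 1 dose of AMG 330 or pembrolizumab". Protocol 9.3.1 says the same.

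Two other sets are defined. One is for DLT-evaluable subjects. The other is for PK, where subjects must also "have at least 1 PK sample collected". There is no antibody counterpart.

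In cohort 1 pembrolizumab starts late and conditionally (SAP 3.1.1): "If the subject has not experienced a DLT by day 14, they will receive pembrolizumab on day 15". Under protocol 4.2.1, a cohort 1 sentinel with a DLT in the first 14 days does not go on to the combination. Cohort 2 receives pembrolizumab on day 1 (SAP 3.1.2).

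**The concern.** A percentage of subjects who develop antibodies is informative only if its denominator holds people in whom development could have been seen. That takes exposure to the drug and a result after exposure. The default set requires neither for the drug in question.

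Two groups can enter wrongly:

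- **No post-dose result.** Subjects treated with a drug but without a later antibody result for it. This can affect both drugs.
- **Never given pembrolizumab.** Cohort 1 subjects who received AMG 330 and stopped, or had a DLT, before day 15. This affects only the anti-pembrolizumab rate. It falls on cohort 1, because cohort 2 starts pembrolizumab on day 1, and the SAP reports the rate by cohort.

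Anti-AMG 330 antibody formation is a secondary endpoint, and protocol 2.2.2.2 reports loss of exposure from anti-drug antibodies in the nonclinical work. With about 20 subjects in total, each misplaced subject moves the percentage visibly.

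**Working it through.** **The plan's own figure.** The documents state no expected antibody rate and no expected number untested, so there is nothing on this point to reproduce. The sample-size figure does reproduce (1 − 0.75^6 = 0.822, stated as 82%) and is not affected.

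**Formula.** Let N be the Safety Analysis Set count (overall or in a cohort), m the subjects in it with no dose of the drug or no post-dose result, and x the subjects who develop antibodies. Take development to require a post-dose positive.

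- Reported rate: x/N
- Rate among evaluable subjects: x/(N−m)
- Ratio of reported to evaluable: (N−m)/N

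**Inputs from the documents.** About 20 subjects in total; at least 10 cohort 1 subjects treated up to day 28 (SAP 3.2); pembrolizumab first given on day 15 in cohort 1 (SAP 3.1.1). Subjects treated up to day 28 on schedule have passed the day 15 dose. Cohort 1 subjects who never receive pembrolizumab therefore come on top of those 10.

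**Assumed inputs.** All values of x and m below.

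| Case | x | N | m | x/N | x/(N−m) | Ratio |
|---|---|---|---|---|---|---|
| Anti-AMG 330, overall | 4 | 20 | 1 | 20.0% | 21.1% | 0.95 |
| Anti-AMG 330, overall | 4 | 20 | 2 | 20.0% | 22.2% | 0.90 |
| Anti-pembrolizumab, cohort 1 | 1 | 13 | 3 | 7.7% | 10.0% | 0.77 |

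The last row is 10 subjects who reached pembrolizumab plus 3 who did not, a relative understatement of 1 − 10/13 = 23%.

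**No positives (x = 0).** The point estimate is 0% on either denominator. SAP 9.1 specifies Clopper-Pearson intervals for proportions. No level is given for antibodies, so I use the 80% level that SAP 9.5.2 sets for response. The upper limit on n subjects is then 1 − 0.1^(1/n):

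- n = 20: 10.9%; n = 18: 12.0%
- n = 13: 16.2%; n = 10: 20.6%

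**How likely is m ≥ 1 for pembrolizumab in cohort 1?** If a fraction q of treated cohort 1 subjects never reach day 15, the chance that at least one of the first 10 is such a subject is 1 − (1−q)^10. This gives 40%, 65% and 89% for assumed q of 5%, 10% and 20%.

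**The case against.** The strongest reply is that SAP section 6 fixes the population and does not say how missing results are handled. Where the SAP wants missing to mean failure it says so, as for response in SAP 9.5.2: "Subjects missing post baseline disease assessments will be considered not to have achieved response". SAP 9.6.7 has no such sentence, so a programmer could reasonably use subjects with a result as the denominator. This stands in part. A reader might infer that the SAP plans to classify untested subjects as antibody-negative, and the documents do not support that. The dilution follows only from applying the default set as written.

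Four further points on that side also stand:

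- **Anti-AMG 330 sampling.** The schedules appear to include end-of-treatment and safety follow-up samples, although the table columns are partly broken in the text. Protocol 6.2.2.1 and 8.1.3 call for those visits after early discontinuation. Missing results should then come mainly from deaths, withdrawals, losses to follow-up and missed samples.
- **Anti-pembrolizumab status.** The endpoint is exploratory. Samples are stored and assayed at the sponsor's discretion (protocol Table 11-1), and SAP section 1 makes the analysis conditional on need.
- **Direction.** Nothing defines *develop* for subjects positive at baseline. Counting them as positive would push the rate up.
- **Consequence.** No hypothesis is tested and no decision rule uses the antibody rate.

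A reader might also infer a large understatement from protocol 4.3, where 39 of 49 first-in-human subjects were evaluable (10/49 = 20% were not). That concerns response, not antibody sampling, and cannot stand in for m.

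None of this removes the point. The SAP's own default, read as written, gives the diluted percentage, and the PK set shows that the SAP requires a sample where it intends to.

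**Conclusion.** The concern holds in limited form. With no analysis set named in SAP 9.6.7, the default denominator admits subjects without a post-dose antibody result. For anti-pembrolizumab it also admits cohort 1 subjects who never had the drug. If at least one such subject and at least one positive exist, the reported percentage equals the evaluable-subject percentage times (N−m)/N. With no positives, only the upper limit of any confidence interval is affected.

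The size cannot be derived from the documents. For the secondary anti-AMG 330 endpoint it is probably small: one or two untested of 20 would shift an assumed 20.0% to 21.1% or 22.2%. For the exploratory anti-pembrolizumab rate in cohort 1 it could be larger in relative terms (7.7% versus 10.0% with three never-dosed subjects), but that analysis may not be run. These figures rest on assumed counts and on development meaning a post-dose positive. They illustrate the mechanism and are not estimates of the bias.

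**What to change.** In SAP 9.6.7:

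- Set the denominator for each drug as Safety Analysis Set subjects with at least one dose of that drug and at least one post-dose antibody result for it.
- Define *develop* as positive post-dose and either negative or without a result at baseline.
- Show, overall and by cohort, the number not evaluable for each drug.

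The cost is two SAP sentences and one added count in the table. No new samples or data are needed. The downside is a percentage that may look slightly less favourable.

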## 9.6.8 Exposure to Investigational Product

Details of AMG 330 and pembrolizumab administration will be listed for every subject.

Descriptive statistics will be produced to describe the exposure to AMG 330 and pembrolizumab. The number of cycles initiated, completed, discontinued, and re-started will be summarized. In addition, the duration of therapy and the cumulative dose may be summarized by cycle and overall. The number and percentage of subjects with dose modifications (eg, dose changes, dose interruptions) and reasons for modification will be summarized.

## 9.6.9 Exposure to Other Protocol-required Therapy

Details of dexamethasone and tocilizumab administration may be listed for every subject.

Protocol Number: 20170646

Date: 25 August 2020 Page 24 of 35

# 9.6.10 Exposure to Concomitant Medication

The number and percent of subjects receiving concomitant medications from study day 1 through AMG 330 or pembrolizumab safety follow-up (SFU), whichever is later, will be summarized by preferred term or category or indication for each cohort as coded by the World Health Organization Drug (WHODRUG) dictionary.

### 9.7 Other Analyses

[figure not shown]
## 9.7.1 Analyses of Pharmacokinetic Endpoints

## 9.7.1.1 Pharmacokinetic Analysis of AMG 330

AMG 330 PK parameters (eg,: half-life, steady state concentration, volume of distribution, and clearance) will be determined as appropriate from the time-concentration profile using standard non-compartmental methods and will be listed for individual subjects. Serum concentrations below the lower limit of quantifications will be set to zero for the estimation of the pharmacokinetic parameters for each subject and for the calculation of the summary statistic for each time point. Analyses will be performed based on Pharmacokinetic Analysis Set.

# 9.7.1.2 Pharmacokinetic Analysis of Pembrolizumab

Pembrolizumab serum samples will be taken as listed in Schedule of Assessment of protocol. Summary statistics, including mean, standard deviation, CV%, median, range (Minimal, Maximal), geometric mean and CV% of geometric mean will be computed. Individual concentration-time data will be tabulated and presented in PK appendix. Analyses will be based on Pharmacokinetic Analysis Set.

### 10. Changes From Protocol-specified Analyses

There are no changes to the protocol-specified analyses.

Protocol Number: 20170646

**Date:** 25 August 2020 Page 25 of 35

# 12. Prioritization of Analyses

There is no prioritization of analyses.

# 13. Data Not Covered by This Plan

None

**Protocol Number:** 20170646

**Date**: 25 August 2020 Page 29 of 35

# 14. Appendices

**Protocol Number:** 20170646

**Date**: 25 August 2020 Page 30 of 35

**Protocol Number:** 20170646

**Date:** 25 August 2020 Page 31 of 35

Protocol Number: 20170646

Date: 25 August 2020

Page 32 of 35

# Appendix B. Reference Values/Toxicity Grades

The Common Terminology Criteria for Adverse Events (CTCAE) version 5.0 will be used.

Refer to protocol Sections Table 6-3, Table 6-4 and Table 6-5.

Notable values for vital signs and physical measurements are defined in the following table.

Table 14-1. Notable Abnormalities of Vital Signs and Physical Measurement

Vital Signs or Physical Measurements		Notable Abnormalities
Heart rate (bpm)		> 120
		< 50
Blood pressure (mmHg)	Systolic	≥ 160
		≤ 90
	Diastolic	≥105
		≤ 50
Body temperature (°C)		> 39
Weight (kg)		Change from baseline ≥ 10% (in both directions)

**Protocol Number:** 20170646

**Date:** 25 August 2020 Page 33 of 35

# Appendix C. Eastern Cooperative Oncology Group (ECOG) Performance Status

Grade	Description	
0	Fully active, able to carry on all pre-disease performance without restriction	
1	Restricted in physically strenuous activity but ambulatory and able to carry out work of a light or sedentary nature, eg, light house work, office work	
2	Ambulatory and capable of all selfcare but unable to carry out any work activities. Up and about more than 50% of waking hours	
3	Capable of only limited selfcare, confined to bed or chair more than 50% of waking hours	
4	Completely disabled. Cannot carry on any selfcare. Totally confined to bed or chair	
5	Dead	

Source: Oken et al, 1982

**Product:** AMG 330 + Pembrolizumab **Protocol Number:** 20170646

**Date:** 25 August 2020 Page **34 of 35** 

Appendix D. European LeukemiaNet (ELN) Response Criteria in Acute Myeloid Leukemia (2017)

Category	Definition	Comment				
Response	Response					
CR without minimal residual disease (CR MRD -)	If studied pretreatment, CR with negativity for a genetic marker by RT–qPCR, or CR with negativity by MFC	Sensitivities vary by marker tested, and by method used; therefore, test used and sensitivity of the assay should be reported; analyses should be done in experienced laboratories (centralized diagnostics)				
Complete remission (CR)	Bone marrow blasts < 5%; absence of circulating blasts and blasts with Auer rods; absence of extramedullary disease; ANC ≥ 1.0 x 10  /L (1000/µL); platelet count ≥ 100 x 10  /L (100 000/µL)	MRD + or unknown				
CR with incomplete hematologic recovery (CRi)	All CR criteria except for residual neutropenia (< 1.0 x 10  /L [1000/μL]) or thrombocytopenia (< 100 x 10  /L [100 000/μL])					
Morphologic leukemia-free state (MLFS)	Bone marrow blasts < 5%; absence of blasts with Auer rods; absence of extramedullary disease; no hematologic recovery required	Marrow should not merely be "aplastic"; at least 200 cells should be enumerated or cellularity should be at least 10%				
Partial remission (PR)	All hematologic criteria of CR; decrease of bone marrow blast percentage to 5 to 25%; and decrease of pretreatment bone marrow blast percentage by at least 50%	Especially important in the context of phase 1/2 clinical trials				
Treatment failure	Treatment failure					
Primary refractory disease	No CR or CRi after 2 courses of intensive induction treatment; excluding patients with death in aplasia or death due to indeterminate cause	Regimens containing higher doses of cytarabine are generally considered as the best option for patients not responding to a first cycle of 7+3; the likelihood of responding to such regimens is lower after failure of a first				
Death in aplasia	Deaths occurring ≥ 7 days following completion of initial treatment while cytopenic; with an aplastic or hypoplastic bone marrow obtained within 7 days of death, without evidence of persistent leukemia					
Death from indeterminate cause	Deaths occurring before completion of therapy, or < 7 days following its completion; or deaths occurring ≥ 7 days following completion of initial therapy with no blasts in the blood, but no bone marrow examination available					

Page 1 of 2

Footnotes defined on next page of table

